9.1. Sample Size and Power Considerations

Assuming an expected dropout rate of 10%, it is recommended that 400 patients be enrolled so that 360 evaluable patients complete the study. These conclusions are based on a review of the relevant literature, as follows.

Based on previous studies of an exacerbation-prone COPD cohort ([Dransfield et al 2013](#), [Vogelmeier et al 2011](#), [Wedzicha et al 2013](#), [Wedzicha et al 2016](#)), it is expected that 91 (range, 73 to 110) CE-COPD events will occur over the 12-week evaluation period in this study based on reported CE-COPD exacerbation rates of 1.05 and 1.14 events per year. Furthermore, it is expected that 14% (14) of total exacerbations will be severe.

This sample size (ie, n=400 patients, 73 to 110 CE-COPD events) is considered adequate for the fulfillment of the study objectives to evaluate the relationship of albuterol use, inspiratory flow, SDI, and TDS data associated with a subsequent CE-COPD event. Per a previous study ([Jenkins et al 2013](#)), a statistically significant relationship was established between daily SABA usage and subsequent CE-COPD.

In the present study, approximately 73 to 110 CE-COPD events are desired because the model's fitting of the current study involves the analysis of multiple predictors as described in more detail below. Because the largest model considered has 7 covariates, it is desirable to have at least 70 events. The probability to observe at least 70 CE-COPD events is higher than 0.99.

Risk models published in the literature have typically included between 4 and 6 covariates/risk factors ([Bateman et al 2015](#), [Greenberg et al 2012](#), [Quezada et al 2016](#)) to examine the relationship between possible risk factors and a disease. When there is more than 1 covariate (risk factor) in the model, multiple logistic regression may be used to estimate the relationship of a specific covariate of interest (ie, albuterol use) to a primary outcome (ie, CE-COPD), adjusting for the other/remaining covariates (risk factors). In this case, the required sample size to estimate such a relationship is greater than that for univariate logistic regression.

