9.5.2.1. Endpoint Analysis

The relationship between albuterol usage and CE-COPD will be analyzed as follows, without controlling for multiplicity.

The multiple device-use-measures will be used as predictors of CE-COPD in the following stepwise selection logistic regression models to select significant predictors in a forward manner:

1. albuterol usage
2. albuterol usage + inspiratory flow values
3. albuterol usage + SDI
4. albuterol usage + TDS
5. albuterol usage + inspiratory flow values + SDI

6. albuterol usage + inspiratory flow values + TDS

The selection of covariates will be performed at the 0.2 level.

Demographic variables and disease state information collected at study enrollment will also be considered as predictors. Because the device-use-measures will be collected continuously over time, these measures could be used to derive many potential predictors of risk. For example, with respect to albuterol use, a subject using the inhaler 3 times in the span of a 2-day or 3-day period could be a strong predictor of a CE-COPD, but a better marker for risk might be 10 times in the span of a week. There are no prior robust data to inform these decisions; 1 possible benefit of this work will be to examine the relationship between multiple functional forms for the device-use-measures to determine which forms have predictive power.

Furthermore, the effect of including interaction terms in the model (ie, testing the assumption of additivity of predictors on the log odds scale) will also be studied. Pair-wise interactions will be assessed at the 0.01 significance level to avoid weak interaction signals that would potentially not translate when applying the risk score to new cohorts. Goodness-of-fit tests may be applied to make sure that the finally selected model fits the data closely. The C-statistic ([Hosmer et al 2013](#)) will be used to compare the goodness of fit of various logistic regression models in terms of how well the predictor(s) discriminate between patients with and without CE-COPD.

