2.3. Sample Size and Power Considerations

Assuming an expected dropout rate of 10%, it is recommended that 400 patients be enrolled so that 360 evaluable patients complete the study. These conclusions are based on a review of the relevant literature, as follows.

Based on previous studies of an exacerbation-prone COPD cohort ([Dransfield et al 2013](#), [Vogelmeier et al 2011](#), [Wedzicha et al 2013](#), [Wedzicha et al 2016](#)), it is expected that 91 (range, 73 to 110) CE-COPD events will occur over the 12-week evaluation period in this study based on reported CE-COPD exacerbation rates of 1.05 and 1.14 events per year. Furthermore, it is expected that 14% (14) of total exacerbations will be severe.

This sample size (ie, n=400 patients, 73 to 110 CE-COPD events) is considered adequate for the fulfillment of the study objectives to evaluate the relationship of albuterol use, inspiratory flow, SDI, and TDS data associated with a subsequent CE-COPD event. Per a previous study ([Jenkins et al 2013](#)), a statistically significant relationship was established between daily SABA usage and subsequent CE-COPD.

In the present study, approximately 73 to 110 CE-COPD events are desired because the model's fitting of the current study involves the analysis of multiple predictors as described in more detail below. Because the largest model considered has 7 covariates, it is desirable to have at least 70 events. The probability to observe at least 70 CE-COPD events is higher than 0.99.

Risk models published in the literature have typically included between 4 and 6 covariates/risk factors ([Bateman et al 2015](#), [Greenberg et al 2012](#), [Quezada et al 2016](#)) to examine the relationship between possible risk factors and a disease. When there is more than 1 covariate (risk factor) in the model, multiple logistic regression may be used to estimate the relationship of a specific covariate of interest (ie, albuterol use) to a primary outcome (ie, CE-COPD), adjusting for the other/remaining covariates (risk factors). In this case, the required sample size to estimate such a relationship is greater than that for univariate logistic regression.

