Clinical Exacerbation of COPD Status: Clinical exacerbation of COPD status is an indicator of whether or not a patient experienced a CE-COPD during study follow-up (Yes, No).

Clinical Exacerbation of COPD Rate: The percentage of patients who experience at least 1 moderate or severe CE-COPD at the end of study follow-up.

Recurrent Clinical Exacerbation of COPD Rate: The percentage of patients who experience more than 1 moderate or severe CE-COPD at the end of study follow-up.

Time to Clinical Exacerbation of COPD: Time, in days, from Study Day 1 to the Date of Symptom Peak plus 1.

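### The >0.99 assurance of at least 70 events counts repeat exacerbations; for a logistic model of patients with versus without CE-COPD the plan's own inputs give about 80 patients and a probability of about 0.92

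*Protocol*

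**What the plan says.** Protocol 9.1 starts from 400 enrolled and 360 evaluable patients: "it is recommended that 400 patients be enrolled so that 360 evaluable patients complete the study". From "reported CE-COPD exacerbation rates of 1.05 and 1.14 events per year" it concludes that "it is expected that 91 (range, 73 to 110) CE-COPD events will occur over the 12-week evaluation period". It then sets the requirement, which SAP 2.3 repeats: "Because the largest model considered has 7 covariates, it is desirable to have at least 70 events". The multiplier is the usual logistic-regression rule of ten events per predictor. The assurance follows: "The probability to observe at least 70 CE-COPD events is higher than 0.99". The synopsis carries the same text.

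Protocol 9.5.2.1 lists six forward-stepwise logistic models and compares them by the C-statistic, "in terms of how well the predictor(s) discriminate between patients with and without CE-COPD". SAP 7.5.1 says that a patient can have more than one CE-COPD and defines a yes/no status per patient: "Clinical exacerbation of COPD status is an indicator of whether or not a patient experienced a CE-COPD during study follow-up".

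The SAP does not specify these models. SAP 7.5.3 passes the predictive modelling to a separate report, and SAP 7.5.2.3 gives a patient-day logistic model as one possibility.

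**The concern.** The rule of ten concerns the number of outcomes in the rarer class of the logistic model. If the model separates patients who had a CE-COPD from those who did not, the relevant number is patients with at least one event. An annual event rate multiplied by patient-time gives total events instead, and that total is larger whenever some patients have more than one. Neither document converts one into the other.

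This probability is the only numerical assurance given for the sample size. If it belongs to a different count from the one the model uses, readers are told that the target is almost certain to be reached when it is only likely. The same text is written as though it covered SDI and TDS, which are each measured in only about 100 patients.

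**Working it through.** **Inputs (Protocol 9.1 and 9.5.1).** 360 evaluable patients (400 × 0.90); rates 1.05 and 1.14 per year, midpoint 1.095; 12 of 52 weeks; 7 covariates × 10 = 70; SDI and TDS subsets of 100 each.

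**Step 1: reproduce the plan's figure.**
- Events per patient: 1.095 × 12/52 = 0.2527.
- Expected events: 360 × 0.2527 = 90.97, which rounds to 91.
- Poisson with mean 90.97: 2.5% and 97.5% quantiles 73 and 110; P(≥70) = 0.9901.

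The 91, the range and the >0.99 all match. A binomial count with the same mean has a 95% range of 75 to 107, which does not match. The plan does not name the Poisson distribution; it is inferred from this agreement. At the lower rate of 1.05 the mean is 87.2 events and P(≥70) is 0.974, so even for events the >0.99 does not hold across the plan's own two rates.

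**Step 2: convert to patients with at least one event.**
- P(at least one event) = 1 − exp(−0.2527) = 0.2233.
- Expected patients: 360 × 0.2233 = 80.4.
- Binomial(360, 0.2233): 95% range 65 to 96; P(≥70) = 0.918.

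| Rate per year | Expected patients with an event | P(≥70) |
|---|---|---|
| 1.05 | 77.5 | 0.847 |
| 1.095 | 80.4 | 0.918 |
| 1.14 | 83.3 | 0.960 |

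**Step 3: sensitivity to assumptions not in the documents (midpoint rate).**
- If each of the 40 dropouts contributes half of the 12 weeks, the risk per dropout is 1 − exp(−0.1263) = 0.1187. That adds 4.7 patients, for a total of 85.1, and P(≥70) = 0.974.
- If all 400 were followed for the full 12 weeks, 89.3 patients are expected and P(≥70) = 0.993. This is an upper bound that sets aside the plan's 10% dropout.
- If rates vary between patients (negative binomial, 360 patients), dispersion 0.25, 0.5 and 1 gives 78, 76 and 73 patients and P(≥70) of 0.87, 0.81 and 0.65.

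**Step 4: the accelerometer subsets.** Models 3 to 6 contain SDI or TDS.
- Expected patients with an event: 100 × 0.2233 = 22.3; 95% range 14 to 31.
- At ten per variable: 22.3 / 10 = 2.2, so about 2 terms.
- Counting events instead: 100 × 0.2527 = 25.3, also about 2 terms.

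With one albuterol term, models 5 and 6 have 1 + 4 flow values + 1 = 6 terms. With the three named albuterol parameters they have 8.

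**The case against.** **The sentence is arithmetically correct.** It speaks of events, and for events it reproduces at 0.9901. That stands. The fault lies in applying the figure to a model with another unit.

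**The patient unit is an inference.** It rests on the C-statistic clause in Protocol 9.5.2.1, supported by the status definition in SAP 7.5.1. The albuterol parameters are anchored to individual events. SAP 7.1.2.2 and 7.5.2.1 keep repeat events, and in the patient-day model of SAP 7.5.2.3 repeats could count as outcomes. The SAP prevails where it differs from the protocol. This also stands, and it is why the first request is to state the unit. It does not rescue the text as written: SAP 2.3 still repeats the assurance, and the patient-day model is only a possibility.

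**Dropouts are not lost entirely.** SAP section 7 uses all enrolled patients, and SAP 4.6 keeps data collected before withdrawal. That is a fair reason to quote about 0.97 beside 0.92, with its assumption. It remains below 0.99.

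Three stronger readings are tempting, and the documents do not support them:
- *The sample size fails the rule.* The expected 80 patients exceed 70, and the plan calls 70 desirable under a rule of thumb.
- *Seven covariates match no listed model.* Model 2, with three albuterol parameters and four flow values, has exactly seven terms and can be fitted in the full cohort.
- *Lowering the target to the six terms of model 5 or 6 would restore the >0.99.* Those models need SDI or TDS, so they draw on about 100 patients and about 22 with an event, far short of 60.

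**Conclusion.** The point holds, as a mismatch of units. The >0.99 describes total exacerbations. For the patient-level models that Protocol 9.5.2.1 describes, the plan's inputs give about 80 patients with a CE-COPD (65 to 96) and about a 0.92 probability of reaching 70. That probability runs from 0.85 to 0.96 over the two quoted rates. It is about 0.97 at the midpoint rate if dropouts contribute half their time.

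These figures rest on independent Poisson events at a common rate, the same model that reproduces the plan's numbers. Variation in rate between patients would lower them. For a 7-term full-cohort model such as model 2, ten per variable is still met on average; only the near-certainty is lost. The assurance does not extend to models 3 to 6, whichever unit is chosen.

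**What to change.** In the synopsis, Protocol 9.1 and SAP 2.3:

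1. State the unit of analysis of the predictive logistic models (patient, event or patient-day), and carry it into the separate report named in SAP 7.5.3.
2. For the patient-level model, replace the event figure with about 80 patients with at least one CE-COPD (95% range 65 to 96) and P(at least 70) of about 0.92. State that this uses 360 patients, and give about 0.97 under the half-follow-up assumption for dropouts. If a patient-day model is chosen, derive the probability for that unit.
3. Say that the 7-covariate, 70-event statement applies only to models fitted in the full cohort, and name the seven terms.
4. For models 3 to 6, state about 22 patients with an event (95% range 14 to 31), which supports about 2 terms under the same rule.

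The cost is restated figures and a few sentences in three places. No extra patients, visits or data are needed.

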Patients will receive initial eMDPI devices at visit 2 based on anticipated usage pattern. In the event that additional eMDPI devices are needed, patients will be required to visit the investigational center to receive them. Patients will be instructed to return all inhalers to the investigational center at the last study visit or earlier, including at the early termination visit, as well as at any other point if there is a problem with the inhaler. At the last study visit or early termination, patients will be queried for adverse events, concomitant medications, and COPD exacerbations; a physical examination will be completed; and the patient will subsequently be discharged from the trial.

Two subsets of patients who agree to participate at specific investigational centers and wear an accelerometer either on the ankle to measure TDS (n=100) or on the wrist to measure SDI (n=100) will be instructed on the proper use of these devices at the baseline visit (visit 2). The devices will be worn throughout the 12-week intervention period and will be returned to the investigational center at the final visit or upon early termination (visit 5).

The end of study is defined as the last visit of the last patient.

The study duration will be approximately 9 months.

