6.1.3. Inspiratory Flow Values Upon Albuterol Dosing

Inspiratory flow values will include (1) maximal inhalational flow (MIF), (2) inhalational volume, (3) inhalational duration and (4) time to MIF. The inhalational flow data will be downloaded using extraction software directly from eMDPI devices collected from the patients at their final study visit after return of the device to the depot.

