The number of events per variable has been suggested as a criterion for the size of a data set ([Harrell et al 1984](#), [Laupacis et al 1997](#), [Peduzzi et al 1996](#),). The rule of thumb when building logistic regression models is 1 predictor variable for every 10 events ([Peduzzi et al 1996](#), [Vittinghoff and McCulloch 2007](#)). Therefore, this sample size would be adequate for predicting the primary outcome (CE-COPD) using multiple logistic regression, including the covariate of primary interest (ie, albuterol use) and the remaining multiple predictors (inspiratory flow values, SDI, and TDS) as potential risk factors for CE-COPD in the model for this patient population.

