9.5. Endpoint Analysis

9.5.1. Endpoints

The endpoints of the trial are the primary outcome measure (ie, CE-COPD) and the primary outcome predictor (ie, albuterol use) alone or in combination with secondary predictors (ie, other study data, including inspiratory flow, SDI, TDS, disease state at baseline, and demographics at baseline) of CE-COPD. These predictors of CE-COPD will be modeled to determine which patterns best predict the subsequent development of CE-COPD. For albuterol use, examples of correlates of CE-COPD of interest include (1) the total number of inhalations in the days preceding the peak of a CE-COPD, (2) the number of days prior to the peak of a CE-COPD when albuterol use increased, and (3) the number of albuterol uses in the 24 hours preceding a CE-COPD.

Albuterol use and inspiratory flow values are obtained from the eMDPI, SDI is obtained for a subset of patients (n=100) from an accelerometer worn on the wrist, and TDS is obtained for a subset of patients (n=100) from an accelerometer worn on the ankle. Baseline disease state and demographic information will be obtained at screening.

The following 8 surrogate measures of sleep disruption are available from the accelerometer worn on the wrist: (i) sleeptime average total time in bed, (ii) sleeptime average total sleep time, (iii) sleeptime average sleep latency time, (iv) sleeptime average wakening after sleep onset, (v) total time awake at night, (vi) longest sleeptime wake episode, (vii) daytime average minutes asleep, and (viii) longest daytime sleep episode.

The SDI for analysis in this study is the composite endpoint derived from the summation of sleeptime average sleep latency time, longest sleeptime wake episode, and total time awake at night. These 3 surrogate measures were correlated significantly with SABA rescue use (sleeptime average sleep latency time ($r=0.78$), longest sleeptime wake episode ($r=0.73$), and total time awake at night ($r=0.65$) ([Krouse et al 2008](#)).

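### The rule of 10 events per predictor is applied to the events of all 360 evaluable patients, but models 5 and 6 can draw on only about 23–25 events from a 100-patient accelerometer subset

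*Protocol*

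**What the plan says.** Protocol 9.1 and SAP 2.3 carry the same sample-size text. With 10% dropout, 400 enrolled patients leave 360 evaluable. At reported rates of 1.05 and 1.14 exacerbations per year, 91 events (range 73 to 110) are expected over 12 weeks. The criterion is events per variable: "The rule of thumb when building logistic regression models is 1 predictor variable for every 10 events". The target follows from it: "Because the largest model considered has 7 covariates, it is desirable to have at least 70 events", with the probability of reaching 70 put above 0.99. The conclusion is "Therefore, this sample size would be adequate for predicting the primary outcome (CE-COPD) using multiple logistic regression", covering albuterol use and "the remaining multiple predictors (inspiratory flow values, SDI, and TDS) as potential risk factors for CE-COPD".

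The accelerometer measures come from subsets. Protocol 9.5.1 states that "SDI is obtained for a subset of patients (n=100) from an accelerometer worn on the wrist" and gives the same number for TDS at the ankle. Protocol 3.1 has patients "wear an accelerometer either on the ankle to measure TDS (n=100) or on the wrist to measure SDI (n=100"). SAP 3.4 and 3.5 further restrict these analysis sets to patients whose device data were successfully downloaded.

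Protocol 9.5.2.1 lists six models with forward stepwise selection at the 0.2 level. Model 5 is "albuterol usage + inspiratory flow values + SDI"; model 6 has TDS in place of SDI. The flow values are four quantities: "Inspiratory flow values will include (1) maximal inhalational flow (MIF), (2) inhalational volume, (3) inhalational duration and (4) time to MIF" (Protocol 6.1.3). Baseline disease state and demographic variables are further candidates.

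SAP 7.5.3 and 20.4 pass the predictive modelling to a data analytics group and a separate report. SAP 2.3 keeps the adequacy statement unchanged.

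**The concern.** The rule is applied to one event count, and the conclusion is drawn for models that cannot use that count. A regression containing SDI or TDS can be fitted only to patients who have the measure. Protocol 9.3 plans no imputation unless the analysis plan says otherwise, and the rules in SAP 4.6 fill in missing days only from a patient's own accelerometer data. Neither document gives an event count for a subset.

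This text is the only sample-size basis offered for the predictive models. Anyone relying on it would believe that the models combining albuterol, flow and an accelerometer measure satisfy the plan's own criterion. By that criterion they would be fitted with too few events for their number of candidate terms, and their coefficients and discrimination should be read accordingly.

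**Working it through.** **Inputs.** Rates 1.05 and 1.14 per year (midpoint 1.095), 12 weeks, 360 evaluable patients, 10% dropout and 10 events per variable (Protocol 9.1); 100 patients per accelerometer subset (Protocol 3.1, 9.5.1); four flow values (Protocol 6.1.3); model list (Protocol 9.5.2.1).

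**Assumptions.** Events are Poisson, the cohort rate applies in the subsets, and each subset has 90 evaluable patients (10% dropout) to 100 (none). Failed downloads would lower this further.

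**1. Reproduce the plan's figure.** Events = N × (12/52) × rate.

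- N = 360: 360 × 0.23077 × 1.095 = 90.97, which rounds to 91. The Poisson 95% interval is 73 to 110, exactly the stated range.
- N = 400: 101.1, which does not match. The 91 is therefore the count for all 360 evaluable patients.
- P(at least 70 events) at N = 360 is 0.990 at the midpoint rate and 0.974 at 1.05 per year.

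**2. Events in one subset.** Expected patients with at least one event = N × (1 − exp(−rate × 12/52)).

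| N | Rate per year | Events | Patients with an event |
|---|---|---|---|
| 90 | 1.05 | 21.8 | 19.4 |
| 90 | 1.095 | 22.7 | 20.1 |
| 100 | 1.095 | 25.3 | 22.3 |
| 100 | 1.14 | 26.3 | 23.1 |

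Both counts are shown because total events suit a patient-day analysis such as the one sketched in SAP 7.5.2.3, while patients with an event suit a one-row-per-patient model.

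**3. Models 5 and 6.** One albuterol term + four flow values + SDI or TDS = 6 candidate covariates, so the rule asks for 60 events.

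- Midpoint rate: 22.7/6 = 3.8 to 25.3/6 = 4.2 per variable.
- Over the stated rates: 21.8/6 = 3.6 to 26.3/6 = 4.4. By patients with an event: 19.4/6 = 3.2 to 23.1/6 = 3.9.
- P(at least 60 events) is at most 1.3 × 10⁻⁸.
- Flow counted as one covariate (3 in all, 30 events needed): 22.7/3 = 7.6 to 25.3/3 = 8.4 at the midpoint rate. P(at least 30 events) is 0.06 to 0.26 over the stated rates.

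Six is a minimum. Protocol 6.1.2 lists three albuterol parameters, and baseline variables come on top.

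**4. Models 3 and 4.** With exactly two terms: 21.8/2 = 10.9 to 26.3/2 = 13.2 by events, and 19.4/2 = 9.7 to 23.1/2 = 11.6 by patients with an event. P(at least 20 events) is 0.68 to 0.91. A third term gives at most 26.3/3 = 8.8.

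**5. Models 1 and 2, full cohort, midpoint rate.** Model 2 with one albuterol term and four flow values: 91.0/5 = 18.2 by events, and 80.4/5 = 16.1 by patients with an event. With three albuterol parameters: 91.0/7 = 13.0 and 80.4/7 = 11.5. Both meet the rule before any baseline term.

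**The case against.** The strongest reply is that the text is a remnant. Protocol Section 9 describes the analysis as foreseen at planning, the SAP prevails where the two differ, and the SAP removes the stepwise models. The covariates that will be fitted with SDI or TDS are therefore unknown, and the aim is exploratory, without multiplicity control. This lowers the urgency. It does not make the sentence true: SAP 2.3 repeats it in current text, and it is tested here against the plan's own rule and figures.

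Second, six is a count of candidates, and forward selection may retain fewer. That is so, and the plan does not say which count its rule refers to. But it sizes the study on the largest model considered, which is a count of candidates.

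Third, flow could be treated as one covariate. The shortfall is then much smaller, but 30 events are still not expected.

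A reader might also infer more than the documents support:

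- *That the plan's figures are miscalculated.* The 91 and its range reproduce exactly. The probability above 0.99 is right for the full cohort at the midpoint rate; its only weakness is the lower rate.
- *That models 3 and 4 are cleared.* They pass by events only with exactly two terms, and SAP 7.4.1 itself gives SDI as three measures plus a composite.
- *That C-statistics will be compared between models fitted to different patients.* Protocol 9.5.2.1 does not say so, and the separate report was not available.

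**Conclusion.** The concern holds for models 5 and 6. The adequacy statement in Protocol 9.1 and SAP 2.3 is wrong for them by the plan's own criterion: 3.8–4.2 events per variable at the midpoint rate (3.6–4.4 over the stated rates) with six candidates, and still short when flow counts as one covariate. Models 3 and 4 are borderline, and the documents do not support a claim of adequacy for them. Models 1 and 2 meet the rule as listed. The problem is a mismatch between the event count and the patients who can be analysed, not an arithmetical slip.

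It would go too far to conclude that the study as a whole is undersized or that its tests are compromised. The comparisons of albuterol use and flow before an exacerbation (SAP 7.1.2.3 and 7.5.2.1) do not depend on the accelerometer subsets.

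The figures rest on the assumptions listed above. A different exacerbation rate in the subsets would move them, but with six candidates the rate would have to be more than double the stated ones: 60 events against 21.8–26.3.

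**What to change.** In Protocol 9.1 and SAP 2.3:

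1. Limit the adequacy statement to the full-cohort albuterol and albuterol-plus-flow models.
2. State the expected events per accelerometer subset: about 23–25, or about 20–22 patients with an event. Make no adequacy claim for models 3 and 4.
3. State that models 5 and 6 fall below the plan's own rule.

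As suggestions only: list the covariates that make up the 7, since the documents do not itemise them and no current model contains both SDI and TDS. In the separate predictive report, compare the C-statistic of any SDI or TDS model with the simpler model refitted in the same subset patients.

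The cost is wording in two sections and, if the last suggestion is taken up, a little extra analysis. No extra patients are needed. The downside is a less favourable stated figure.
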